#### 4.1.6. Selection of Data in the Event of Multiple Records in a Window

Depending on the statistical analysis method, single values may be required for each analysis window. For example, change from baseline by visit usually requires a single value per visit. Unless otherwise noted throughout the rest of the SAP, when a single value is needed, the following rules will be used:

- If > 1 assessment occurs during the same nominal visit, then the record closest to the nominal day for that visit will be selected.
- If there are 2 assessments that are equidistant from the nominal day, then the data of the assessment after the scheduled study day will be used.
- The last measurement will be used if multiple measurements are taken on the same day.

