- Total bilirubin $\geq 1.2 \times \text{ULN}$ (if total bilirubin is $\geq 1.2 \times \text{ULN}$ then direct bilirubin must be $< 1.2 \times \text{ULN}$)
 - Alkaline phosphatase (ALP) $\geq 2.5 \times \text{ULN}$ (or $\geq 5 \times \text{ULN}$ if bone metastases are present and hepatic parenchymal metastases are absent)
 - Aspartate aminotransferase (AST) or alanine aminotransferase (ALT) $\geq 2.0 \times \text{ULN}$.
 - Creatinine clearance $\leq 50 \text{ mL/min}$ measured or calculated by Cockcroft-Gault equation or estimated glomerular filtration rate $\leq 50 \text{ mL/min/1.73 m}^2$ using the modification of diet in renal disease formula.
10. Current or recent history (< 30 days before screening and/or < 45 days before study drug administration) of a clinically meaningful bacterial, fungal, parasitic, or mycobacterial infection.
11. Current, clinically active viral infection.
12. Known human immunodeficiency virus infection, or hepatitis B virus (HBV) or hepatitis C virus (HCV) viremia or at risk for HBV or HCV reactivation. Hepatitis B virus DNA and testing for HCV RNA must be undetectable. At risk for HBV reactivation is defined as HBSAg positive or anti-HBc antibody positive. At risk for HCV reactivation is defined as HCV antibody positive.
13. History or presence of an abnormal electrocardiogram (ECG) that, in the investigator's opinion, is clinically meaningful. Screening QTc interval > 450 milliseconds is excluded (corrected by Fridericia). In the event that a single QTc is > 450 milliseconds, the subject may enroll if the average QTc for the 3 ECGs is < 450 milliseconds. For subjects with an intraventricular conduction delay (QRS interval > 120 milliseconds), the JTc interval may be used in place of the QTc with sponsor approval. The JTc must be < 340 milliseconds if JTc is used in place of the QTc. Subjects with left bundle branch block are excluded.
14. Clinically significant or uncontrolled cardiac disease, including unstable angina, acute myocardial infarction within 6 months from Day 1 of study drug administration, New York Heart Association Class III or IV congestive heart failure, and arrhythmia requiring therapy.
15. History of major stomach or intestinal surgery, or malabsorption syndrome (eg, Crohn's disease or chronic pancreatitis) that would, by clinical judgment, affect the absorption of study drug.

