7.4.5.1. Timed Electrocardiograms

Timed triplicate (separated by 5 minutes) ECGs will be performed at Cycle 1 Day 1 and Cycle 1 Day 15. ECGs will be conducted predose and will be conducted in conjunction with the 2-hour and 4-hour PK timepoints (Section 7.7.1). ECGs should be conducted before but within 30 minutes of the PK blood draw at the corresponding timepoint. The specified postdose timepoint may be adjusted based on emerging PK data.

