9.4.3.4. Electrocardiograms

Descriptive statistics and mean change from baseline will be determined for each ECG parameter at each assessment time. Average of all values before the first dose of study drug will be used as the baseline value. Criteria for clinically notable ECG abnormalities are defined in [Table 15](#).

The abnormal values for subjects exhibiting clinically notable ECG abnormalities will be listed.

Alert ECG values are defined as an absolute value outside the defined range and absolute percentage change > 25% (30% for QRS) interval. The abnormal values for subjects exhibiting alert vital sign abnormalities will be listed.

Outliers of QT, QTcB, and QTcF, defined as absolute values > 450 milliseconds or change from baseline > 30 milliseconds, will also be listed.

Table 15: Criteria for Clinically Notable ECG Abnormalities

Parameter	High Threshold	Low Threshold
QTcF	> 460 msec	< 295 msec
PR	> 220 msec	< 75 msec
QRS	> 120 msec	< 50 msec
QT	> 500 msec	< 300 msec
RR	> 1330 msec	< 600 msec

QTcF = Fridericia correction.

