#### 8.5. Electrocardiograms

Twelve-lead ECGs including PR, QRS, QT, QTcF, and RR intervals will be obtained for each subject during the study in accordance with the schedule of assessments. Descriptive statistics and mean change from baseline will be determined for each ECG parameter at each assessment time. Change and percentage change from baseline will be calculated using the average of all nonmissing values prior to the first dose of study drug as the baseline value.

Criteria for clinically notable ECG abnormalities are defined in [Table 4](#). The abnormal values for subjects exhibiting clinically notable ECG abnormalities will be listed.

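### By default the SAP reduces each postbaseline triplicate ECG to its last tracing and compares it with an averaged baseline, which adds avoidable noise to the ECG summaries

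*SAP*

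**What the plan says.** - **Collection.** Protocol 7.4.5.1: "Timed triplicate (separated by 5 minutes) ECGs will be performed at Cycle 1 Day 1 and Cycle 1 Day 15". The sets are taken predose and alongside the 2-hour and 4-hour PK samples.
- **Default selection rule.** SAP 4.1.6: "Unless otherwise noted throughout the rest of the SAP, when a single value is needed, the following rules will be used". It gives an example of such a need: "For example, change from baseline by visit usually requires a single value per visit". For several readings on one day the rule is: "The last measurement will be used if multiple measurements are taken on the same day".
- **ECG baseline.** SAP 8.5 calculates change "using the average of all nonmissing values prior to the first dose of study drug as the baseline value". Protocol 9.4.3.4 agrees: "Average of all values before the first dose of study drug will be used as the baseline value".
- **Postbaseline ECGs.** SAP 8.5 and Protocol 9.4.3.4 ask for descriptive statistics and mean change for every ECG parameter, separately by assessment time. Neither says how the three tracings of a set become one value.
- **Use.** 12-lead ECGs are part of the primary safety endpoint (Protocol 4.3.1, SAP 2.3.1).

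**The concern.** The protocol collects three tracings at each timed assessment, but the analysis plan has no instruction to use all three after baseline. The general rule fills that gap by keeping the last one. The authors overrode the general baseline rule for ECGs (SAP 4.1.3 takes the last value before dosing, SAP 8.5 takes an average), but wrote no matching override for postbaseline values. Change from baseline is then a single tracing minus a mean of several.

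At stake is the precision of the QTcF and other interval summaries on the two days when ECGs are timed to drug exposure, in cohorts of about 15 subjects.

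**Working it through.** The documents give no figure that depends on this rule, so there is none to reproduce. The check counts the readings used and then compares variances.

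**1. Readings used.** Day 15 has 3 times × 3 tracings = 9 readings per parameter. Day 1 has 3 predose readings (part of baseline) and 2 × 3 = 6 postdose. If each assessment time is kept separate, as SAP 8.5 indicates, the default keeps 3 of 9 on Day 15 and 2 of 6 on Day 1.

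**2. Replicate-level variance of change.** With *m* baseline readings averaged, *k* postbaseline readings averaged and replicate variance s², the variance is s²(1/*m* + 1/*k*), assuming independent replicates. Baseline holds the 3 predose readings (*m* = 3), or 4 if one screening ECG is added (assumed single).

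| *m* | last tracing, *k* = 1 | triplicate mean, *k* = 3 | variance ratio | SD ratio |
|---|---|---|---|---|
| 3 | 1/3 + 1 = 1.333 | 1/3 + 1/3 = 0.667 | 2.00 | 1.41 |
| 4 | 1/4 + 1 = 1.250 | 1/4 + 1/3 = 0.583 | 2.14 | 1.46 |

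These ratios do not depend on the size of s.

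**3. Total variance of a subject's change.** Add a time-to-time variance t², which averaging replicates cannot reduce. With *m* = 4, the screening ECG has weight 1/4 and the predose set, which shares one time effect, has weight 3/4:

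- baseline variance = (1/16 + 9/16)t² + s²/4
- last tracing: t² + s² + baseline variance
- triplicate mean: t² + s²/3 + baseline variance

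The documents give neither SD. Assumed ranges are s = 5 to 10 ms and t = 6 to 8 ms.

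| s, t (ms) | baseline (ms²) | last tracing (ms²) | triplicate mean (ms²) | ratio |
|---|---|---|---|---|
| 5, 8 | 40 + 6.25 = 46.25 | 64 + 25 + 46.25 = 135.25 | 64 + 8.33 + 46.25 = 118.58 | 1.14 |
| 8, 8 | 40 + 16 = 56 | 64 + 64 + 56 = 184 | 64 + 21.33 + 56 = 141.33 | 1.30 |
| 10, 6 | 22.5 + 25 = 47.5 | 36 + 100 + 47.5 = 183.5 | 36 + 33.33 + 47.5 = 116.83 | 1.57 |

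**4. Standard error of mean change, 15 subjects, 8 and 8 ms.** √(184/15) = 3.50 ms against √(141.33/15) = 3.07 ms, a ratio of 1.14.

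**The case against.** The best defence is that SAP 4.1.6 yields to anything noted elsewhere in the SAP, and SAP 8.5 does ask for summaries by assessment time. This stands in part. It answers a tempting stronger reading, that the same-day rule leaves only the last 4-hour tracing of the day (1 of 9 on Day 15) and loses the 2-hour data. SAP 8.5 most naturally keeps predose, 2 hours and 4 hours apart, so that loss would follow only from a strictly by-day reading. But separating the times does not say what to do with three tracings at one time, so the default still applies within each triplicate.

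A reader might also infer that the QT outlier listing (above 450 ms, or change above 30 ms) would fire on the noisier selected tracing. The documents do not support this. SAP 4.1.6 applies only when a single value is needed. A listing of values past a threshold does not need one, and the SAP does not say which record the criteria use. Any false-flag rate also depends heavily on the assumed model. At a replicate SD of 8 ms with no true change, the chance of exceeding 30 ms (last tracing against mean) is 1.4% against 0.6% with a time-to-time SD of 8 ms, but 0.04% against under 0.01% without that component. Screening individual tracings is a defensible safety choice, because averaging can hide one high reading.

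Nor does the eligibility rule show a general averaging convention. Under Protocol 3.3, "the subject may enroll if the average QTc for the 3 ECGs is < 450 milliseconds" applies only after a single QTc above 450 ms.

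Finally, the consequence is bounded. Timed triplicates occur on two days only, no hypothesis is tested, and the QTc discontinuation criterion in Protocol 5.6.3 relies on a repeat ECG rather than on SAP record selection. All of this limits the weight of the point without removing it.

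**Conclusion.** The point holds for the summary tables of postbaseline ECG values and change from baseline on Cycle 1 Days 1 and 15. As written, the plan uses the third tracing of each triplicate against an averaged baseline.

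The cost is precision. The 2.0 to 2.1 ratio for replicate-level variance rests only on independent replicates and on 3 or 4 baseline readings. The 14% to 57% increase in total variance, and the 14% larger standard error in the 8 ms example, rest on SDs that the documents do not supply.

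A reader might take the mismatch between a single tracing and an averaged baseline to bias the mean change. It does not, provided the third tracing does not differ systematically from the other two, and nothing in the documents suggests that it does. Nor are the other tracings lost from the record: they can still appear in Listing 2.10.1.

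**What to change.** In SAP 8.5, and in matching words in Protocol 9.4.3.4, state that:

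- replicate ECGs are averaged at each nominal time point before descriptive statistics and change from baseline are computed;
- predose, 2 hours and 4 hours are summarised separately;
- the last-measurement rule of SAP 4.1.6 does not apply to replicate ECGs;
- individual tracings remain in the listings, and the notable, alert and outlier listings use either individual tracings or means, whichever the sponsor chooses.

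The cost is a few sentences of text. No new data, visits or subjects are needed.

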#### 4.1.7. Cycle Length and Duration

INCB050465 and INCB039110 will be self-administered continuously. One cycle will be approximately 21 days of treatment and subjects will receive treatment in continuous cycles.

Cycle 1 Day 1 is defined as the day of the first dose of the study drug. The date of the Day 1 visit of each cycle recorded on the CRF will be used as the actual Day 1 date of the cycle.

### 4.2. Variable Definitions

#### 4.2.1. Age

Subject age will be calculated as the integer part of the number of years from date of birth to the date of signing the informed consent form, using the following formula:

$$\text{Age} = \text{integer part of } (\{\text{date of informed consent} - \text{date of birth} + 1\} / 365.25)$$

#### 4.2.2. Body Mass Index

Body mass index (BMI) will be calculated as follows:

$$\text{BMI (kg/m}^2\text{)} = (\text{weight [kg]}) / (\text{height [m]})^2$$

#### 4.2.3. Prior and Concomitant Medication

Prior medication is defined as any nonstudy medication started before the first dose of study drug. Concomitant medication is defined as any nonstudy medication that was started as follows:

- Before the first dose of study drug and continuing after the first dose of study drug or
- On or after the first dose of study drug up to within 30 days after last dose of study drug.

For purposes of analysis, all medications will be considered concomitant medications unless the medications can unequivocally be defined as not concomitant.

A prior medication could also be classified as "both prior and concomitant medication" if the end date is on or after first dose of study drug. In the listing, it will be indicated whether a medication is prior-only, concomitant-only, or both prior and concomitant medication.

## **5. STATISTICAL METHODOLOGY**

### **5.1. General Methodology**

Unless otherwise noted, SAS® software (SAS Institute Inc, Cary, NC; Version 9 or later) will be used for the generation of all tables, graphs, and statistical analyses. Descriptive summaries for continuous variables will include, but not be limited to, the number of observations, mean, standard deviation, median, minimum, and maximum. Descriptive summaries for categorical variables will include the number and percentage of subjects in each category.

### **5.2. Treatment Groups**

This is a Phase 1, open-label, dose-escalation study; therefore, there are no randomized treatment groups.

The efficacy endpoints, including ORR, [REDACTED] and change in target lesion size, will be summarized by disease subtype. Change in peripheral blood leukemic cells will only be analyzed for subjects with CLL. All other data, including baseline and safety, will be summarized by dose groups. In the event that several dose regimens tested are deemed substantially below the MTD, these doses may be combined for summary purposes.

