The sponsor may implement alternative regimens such as intermediate doses, intermittent dosing schedules, BID doses, or alternative formulations, depending on PK, PD, and safety results. Based on emerging efficacy and safety data from study INCB 50465-101 as of 02 SEP 2016, 1 recommended regimen that will be evaluated in Parts 2, 3, and 6 is 20 mg QD for 9 weeks, followed by 20 mg once weekly. The 20 mg QD dose provides exposure that is approximately 2-fold greater than the IC_{90} (based on an *in vitro* whole-blood assay) at trough. Furthermore, all 11 NHL subjects who received 20 mg QD have achieved an objective response. However, 24% of all 46 subjects in study INCB 50465-101 as of 02 SEP 2016 discontinued study treatment due to an AE. Among the subjects with an objective response ($n = 20$), 7 (35%) discontinued study treatment due to an AE. Consequently, after administration of 20 mg QD for 9 weeks, the dosing regimen will be reduced to 20 mg once weekly. This once-weekly regimen is proposed to maintain response while providing time off from pathway inhibition, which may reduce the frequency of AEs. Pharmacodynamic data from INCB 50465-101 showed that a single dose of 20 mg exhibited maximal inhibition of AKT in an *ex vivo* pharmacodynamic assay, and PK modeling suggests that 20 mg once weekly will 1) achieve maximal inhibition equivalent to approximately $10 \times IC_{90}$, 2) exceed the IC_{90} for approximately 36 hours, and 3) have minimal to no inhibition for approximately half the dosing interval. This once-weekly regimen is similar to

that of another PI3K inhibitor (copanlisib), which is administered intravenously on Days 1, 8, and 15 of a 28-day cycle, and which achieved 7 objective responses in 9 subjects with non-Hodgkin lymphoma (Patnaik et al 2016). Among the 51 subjects who received study drug, 4 discontinued treatment due to an AE. There were 2 events of Grade 3 noninfectious pneumonitis, 1 event of Grade 3 diarrhea, and no events of colitis.

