- Rituximab 375 mg/m² given on Day 1 and Day 2 of Cycle 1, and on Day 1 of Cycles 2 and 3.
- Ifosfamide 5000 mg/m² continuous IV infusion over 24 hours on Day 3.
 - Mesna should be added to ifosfamide infusion.
- Carboplatin AUC = 5 mg/mL (maximum dose 800 mg) IV infusion on Day 3.
- Etoposide 100 mg/m² IV on Days 3 to 5.

Note: As an alternative to the Protocol-specified dose and schedule, R-ICE may be administered according to institutional practice with medical monitor approval.

If tolerated, the dose of INCB050465 will be escalated to the recommended dose in combination with R-ICE. INCB050465 will be given daily or intermittently and may be continued until a criterion is met for treatment discontinuation. If the starting dose of INCB050465 cannot be combined safely with R-ICE at the schedule described above, the dose of INCB050465 will be reduced to 25% below the dose first administered in combination with R-ICE. Additional dose de-escalation may occur with INCB050465 if DLTs occur with a causality that can be reasonably

assigned to INCB050465. Additional dose de-escalation of INCB050465 and intermittent schedules may be considered if supported by emerging safety, PK, [REDACTED] data in this combination. Following the identification of a tolerable dose of the combination of INCB050465 and R-ICE (a dose less than or equal to the MTD), expanded Cohort L will be opened to further evaluate the safety, efficacy, PK, [REDACTED] as described in [Table 2](#).

Table 2: Part 6 Expansion Cohort

Part	Cohort	Population	# of Subjects	Treatment
6	L	DLBCL ^a	~15	INCB050465 + R-ICE

^a Based on emerging data, the sponsor may decide on the number of subjects with a specific subtype of an indication to be enrolled (eg, non-GCB or GCB).

If ≥ 5 subjects in Cohort L experience DLTs during Cycle 1, further enrollment to the cohort will be stopped, and a lower dose level may be explored.

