9.4. Statistical Analyses

9.4.1. General Methodology

Unless otherwise noted, SAS® software (SAS Institute Inc, Cary, NC; Version 9 or later) will be used for the generation of all tables, graphs, and statistical analyses. Descriptive summaries for continuous variables will include, but not be limited to, the number of observations, mean, standard deviation, median, minimum, and maximum. Descriptive summaries for categorical variables will include the number and percentage of subjects in each category.

Data will be summarized overall and by treatment cohorts based on the dose regimen initially assigned. In the event that several dose regimens tested are deemed substantially below the MTD, these doses may be combined for summary purposes.

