## **2. STUDY INFORMATION, OBJECTIVES, AND ENDPOINTS**

### **2.1. Protocol and Case Report Form Version**

This SAP is based on INCB 50465-101 Protocol Amendment 3 dated 06 MAR 2015 and case report form (CRF) approved 03 FEB 2015. Unless superseded by an amendment, this SAP will be effective for all subsequent Protocol amendments and CRF versions.

[figure not shown]

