### 2.3.2. Secondary Endpoints

- Efficacy as measured by ORR, defined as the proportion of subjects achieving a minor response (MR, only among subjects with Waldenström macroglobulinemia [WM]), partial response (PR), very good partial response (VGPR, only among subjects with WM), and a complete response (CR) to INCB050465 as monotherapy and in combination with INCB039110 based on:
  - International Workshop on Chronic Lymphocytic Leukemia criteria for chronic lymphocytic leukemia (CLL; [Hallek et al 2008](#), [Cheson et al 2012](#)).
  - With International Workshop on Waldenström Macroglobulinemia response assessment for subjects with WM ([Owen et al 2013](#)).
  - Revised response criteria for lymphoma for Hodgkin's lymphoma and non-Hodgkin's lymphoma ([Cheson et al 2014](#)).
- $C_{max}$ ,  $T_{max}$ ,  $C_{min}$ ,  $AUC_{0-t}$ , and  $AUC_{0-\tau}$  at Cycle 1 Day 15 of INCB039110 in combination with INCB050465.
- $C_{max}$ ,  $T_{max}$ ,  $C_{min}$ ,  $AUC_{0-t}$ , and  $AUC_{0-\tau}$  of INCB050465 as monotherapy and in combination with INCB039110.

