### **5.3. Analysis Populations**

#### **5.3.1. Intent-to-Treat/Safety Population**

The intent-to-treat (ITT) or safety population includes all subjects enrolled in the study who received at least 1 dose of any study treatment.

Demographics, baseline characteristics, subject disposition, study drug administration, and all safety and efficacy analyses will be conducted using the ITT/safety population.

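### The SAP supplied predates Part 6, does not carry over the protocol's grouping by treatment cohort, and defines no R-ICE group for the ORR, safety or DLT outputs

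*SAP*

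**What the plan says.** SAP 2.1 bases the plan on Protocol Amendment 3 and adds: "Unless superseded by an amendment, this SAP will be effective for all subsequent Protocol amendments and CRF versions". SAP Table 5 lists one version, the Original of 26 JUN 2015. The protocol supplied includes Amendment 10.

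On grouping, the sentence in SAP 5.2 on the efficacy endpoints, ORR among them, reads "and change in target lesion size, will be summarized by disease subtype". The same section continues: "All other data, including baseline and safety, will be summarized by dose groups". Neither dose group nor treatment regimen is defined. The analysis population (SAP 5.3.1) "includes all subjects enrolled in the study who received at least 1 dose of any study treatment", so R-ICE subjects, who all receive INCB050465, are in it. The SAP's ORR endpoint (2.3.2) runs up to "a complete response (CR) to INCB050465 as monotherapy and in combination with INCB039110 based on" and then lists the response criteria; R-ICE is not named.

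Protocol 9.4.1 has a different rule: "Data will be summarized overall and by treatment cohorts based on the dose regimen initially assigned". SAP 10.1 records no change to protocol-defined analyses.

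On DLTs, SAP 8.2.2 confines the listing to Parts 1 and 2. Protocol 9.4.3.1 plans a listing of first-cycle DLTs with no restriction by part.

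**The concern.** A DLBCL response rate that mixes monotherapy and R-ICE subjects describes no single treatment. R-ICE is active in DLBCL by itself (Protocol 1.1.4), so responses due to chemotherapy could be read as activity of INCB050465 alone.

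Safety is the primary endpoint. A column labelled only by INCB050465 dose could likewise place chemotherapy toxicity beside monotherapy toxicity.

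Part 6 also has its own 3 + 3 dose evaluation. If SAP 8.2.2 is followed, the events on which that evaluation turns are not in the DLT listing.

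No hypothesis is tested (Protocol 9.3), and dose decisions rest on ongoing cohort review (Protocol 5.5.1). What is at stake is therefore the reading of the reported results, not an error rate or the dose decisions themselves.

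**Working it through.** **1. The SAP's own sample size.** SAP 3.3 counts 1 subject, up to 4 + 4 dose levels of 3 to 6, and 4 cohorts of 15. That is 1 + (12 to 24) + (12 to 24) + 60 = 85 to 109, which contains the stated figure of about 90. The SAP adds up for the design it was written for; it is out of date, not miscounted.

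**2. The current design.** Protocol 9.2 maxima: 20 (Part 1) + 12 (Part 2) + 30 (A) + 4 × 15 (B to E) + 12 + 15 (Part 6 and Cohort L) = 149, against about 150 stated. With Cohort D at 30, as in Protocol Table 1, the sum is 164. R-ICE subjects number up to 12 + 15 = 27, which is 27/149 = 18.1% or 27/164 = 16.5% of the study.

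**3. Design side by side.**

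| Item | SAP supplied | Current protocol |
|---|---|---|
| Parts | 3 | 4 (1, 2, 3, 6) |
| Part 3 cohorts | A to D | A to E |
| Cohorts C and D | + INCB039110 (SAP 3, 7.3.1) | monotherapy (4.2.3) |
| Cohort E | not named; the text for D fits it | + INCB039110 |
| Part 6 / Cohort L | not named | + R-ICE |

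**4. Does a dose label identify the regimen?** Not reliably. Protocol 4.2.4 says of Part 6: "If tolerated, the dose of INCB050465 will be escalated to the recommended dose in combination with R-ICE". Protocol 1.7.1 says that one "recommended regimen that will be evaluated in Parts 2, 3, and 6 is 20 mg QD for 9 weeks", followed by weekly dosing. The same INCB050465 dose can therefore be given alone, with INCB039110 or with R-ICE.

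**5. Size of the possible mixing (illustration only).** Inputs:
- Monotherapy DLBCL: 5/14 = 35.7% (Protocol 1.2.4; interim, evaluable subjects).
- R-ICE alone: 63% (Protocol 1.1.4, from a cited trial), with 50% as an alternative.
- m monotherapy DLBCL subjects: 14, or 14 + 15 = 29 if a full Cohort C is added at the same rate.
- r R-ICE subjects with DLBCL: assumed 6, 15 or 27.

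Pooled ORR = (m × p1 + r × p2)/(m + r). Example: (5 + 27 × 0.63)/(14 + 27) = 22.01/41 = 53.7%.

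| m | r | Pooled ORR, p2 = 63% | Excess over 35.7% (points) | Excess, p2 = 50% (points) |
|---|---|---|---|---|
| 14 | 6 | 43.9% | 8.2 | 4.3 |
| 14 | 15 | 49.8% | 14.1 | 7.4 |
| 14 | 27 | 53.7% | 18.0 | 9.4 |
| 29 | 6 | 40.4% | 4.7 | 2.4 |
| 29 | 15 | 45.0% | 9.3 | 4.9 |
| 29 | 27 | 48.9% | 13.2 | 6.9 |

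If p1 = p2 the excess is 0.

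**6. DLT listing.** Protocol 9.4.3.1 covers first-cycle DLTs without limit by part, and Part 6 opens with a 3 + 3 evaluation (4.2.4). SAP 8.2.2 stops at Part 2, so that evaluation is left out. For the expansion cohorts the protocol is itself unclear: 5.5.1 ties DLTs to Cycle 1 of the dose-escalation portion, while 4.2.3 and 4.2.4 stop enrolment in Part 3 cohorts and Cohort L on Cycle 1 DLTs.

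**The case against.** **The protocol rule still applies.** Protocol 9.4.1 asks for treatment cohorts and SAP 10.1 declares no departure, so the regimens may well be kept apart in practice. It is true that the gap lies in the SAP and not in both documents. But SAP 5.2 as written gives a different rule, and SAP 10.1 does not disclose the difference.

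**Dose groups can mean dose levels of the regimen given.** For + INCB039110 this is a fair reading. The SAP separates it from monotherapy in its objectives (2.2) and endpoints (2.3), its missing-causality rule (8.2.1) and a combination-only block in the exposure shell. That split is implied, though not stated for the ORR and AE tables. Nothing comparable exists for R-ICE.

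**The shells.** A reader might infer that their Total column pools all regimens. No shell says so, and Appendix A calls the shells guidelines; they could be run separately by part. The gap is in the text of 5.2.

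**The DLT listing.** A reader might also take Listing 2.7.3, whose title names no part, to contradict SAP 8.2.2. A short title does not contradict the text that sets its scope. Limiting the listing to escalation also follows Protocol 5.5.1, so for the expansion cohorts the difficulty starts inside the protocol. Events would still appear in the AE, SAE and Grade 3 or 4 listings. None of this covers the Part 6 dose evaluation.

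**Cohorts C and D.** They are misdescribed, but no SAP analysis groups by cohort letter, so they are not shown to be misanalysed.

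**The figures are hypothetical.** This stands. Part 6 was to start when the sponsor decided, and no enrolment is reported. The 27-subject case assumes full enrolment with every subject having DLBCL; Protocol 4.2 describes the Part 6 safety assessment as open to B-cell malignancies, while 4.2.4 says DLBCL.

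**Conclusion.** The point holds for the SAP version supplied; SAP 2.1 allows for supersession, and a later version may exist. As written, the SAP describes a superseded design, does not carry over Protocol 9.4.1, defines no R-ICE group and leaves the Part 6 dose evaluation out of the DLT listing. It does not instruct pooling, but nothing in it keeps R-ICE apart.

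The pooled DLBCL ORR overstates monotherapy only if the R-ICE rate is the higher one. Under the illustrative inputs the excess is about 5 to 18 points at 63%, 2 to 9 points at 50% and 0 at equal rates. A reader might conclude that pooling must inflate the rate; the documents do not support this, because the 63% comes from another trial. A reader might also enlarge the shift by counting the 46 − 41 = 5 subjects outside the evaluable set as DLBCL non-responders. Protocol 1.2.4 gives neither their subtype nor the reason.

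The harm is to interpretation of exploratory results. It should be fixed before the tables are produced.

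**What to change.** Issue one SAP amendment that:
- brings SAP 3, 5.2, 7.3.1 and 8.2.2 into line with the current parts and cohorts (C and D monotherapy, E + INCB039110, Part 6 and Cohort L + R-ICE);
- defines treatment groups as monotherapy, + INCB039110 and + R-ICE, by the INCB050465 dose and schedule initially assigned, as Protocol 9.4.1 requires;
- reports ORR by disease subtype within treatment group, and safety by treatment group and dose regimen;
- extends the DLT listing to Part 6 and to the expansion cohorts whose stopping rules use DLTs;
- labels any overall column as pooling different regimens.

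Protocol 5.5.1, 4.2.3 and 4.2.4 must be reconciled on which parts have DLTs.

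No new data are needed. The cost is smaller cells and wider intervals: 5/14 alone has an exact 95% CI of 12.8% to 64.9%, against 37.4% to 69.3% for a pooled 22/41. The narrower interval describes a mixture of treatments, so little is lost. Very small cells can be shown as listings, which SAP 8.1 and 8.2.3 already allow for AE tables.
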